4.5 Multiple comparisons/multiplicity

Three endpoints are listed that are associated with the primary objective. There are no plans to control for multiplicity in the primary objectives as the endpoints are different parameterizations of the same underlying endpoint measured on separate days. This means there is effectively only one primary endpoint, PaO₂/FiO₂ ratio which was used to calculate sample size. The comparison of the differences from baseline to two days (D6/Early Discharge and D15/Early discharge) are of specific interest.

There are no plans to control for multiplicity in the secondary objectives as these hypotheses are considered exploratory. Therefore, any findings will need to be confirmed in subsequent studies.

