2.4 Determination of sample size

The outcome(s) on which the sample size calculation is based upon, is the primary endpoint measurement of oxygenation, defined as ratio of PaO₂/FiO₂.

The target difference is the difference from baseline measured at the primary endpoint (at day 6 and day 15) between the control and the treated group. Given a sample size of 81 participants, 54 on Zilucoplan® and standard of care and 27 on standard of care there would be >85% power to show a significant difference from standard of care at the 2 sided 5% level if the true underlying treatment difference was an 80 point difference (25% of 320, being the mean at hospital admission) in the PaO₂/FiO₂ ratio. This assumes a standard deviation of 105 and a dropout rate of less than 10%.

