Decreasing values of P(A-a) O₂ gradient indicates improvement over time (normal A-a gradient is (Age/4) +4) and in addition increases with higher F_iO₂

No similar statement for a/A PO₂ is appropriate.

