8.1.2 Primary analysis of the primary efficacy endpoint(s)

Summary descriptive statistics for each endpoint and change from baseline for each endpoint, including to follow-up, will be provided by treatment and Nominal Day (D1(Baseline), D2, D6, D15 and Follow-Up).

Each endpoint (PaO₂/F_iO₂ ratio, P(A-a)/O₂ gradient, a/A PO₂ ratio) will be analyzed separately using a Mixed Model Repeated Measures (MMRM) analysis with fixed effects for Baseline, treatment, Nominal Day (using Nominal Days, D6 and D15), Baseline*Nominal Day interaction and treatment*Nominal Day interaction where Nominal Day is categorical. Participant will be fitted as a random effect and an unstructured covariance will be used, unless it fails to converge,

when other covariance structures will be considered. Mean change from baseline to D6 and D15 for each treatment arm and differences between treatments in mean change from baseline to D6 and D15, their 95% confidence intervals and p-values will be estimated directly from the model.

The primary analysis will not adjust for missing data, other than how they are handled in MMRM under the assumption that the data are missing at random. This assumption implies that the behaviour of the post dropout observations can be predicted from the observed endpoints, and therefore the response can be estimated without bias using exclusively the observed data.

The following results from the model will be tabulated:

- LSMEANS (adjusted for baseline levels) and 95% confidence intervals for change from baseline by treatment and Nominal Day for each endpoint (PaO₂/FiO₂ ratio, P(A-a)/O₂ gradient, a/A PO₂ ratio)
- Estimates of the differences between treatments in mean change from baseline, 95% confidence interval and p-value at D6 and D15 for each endpoint (PaO₂/FiO₂ ratio, P(A-a)/O₂ gradient, a/A PO₂ ratio).
- Mean percentage change from baseline will be estimated from the results of the MMRM model for D6 and D15 for each Treatment Arm, together with 95% confidence intervals.

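### The SAP treats PaO2/FiO2 as the only real primary endpoint but does not say whether D6, D15, either or both decides it, so the 5% level and >85% power hold only for one unnamed day

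*SAP*

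**What the plan says.** SAP 2.2.1.1 and 8.1 list three primary endpoints from the same arterial blood gas: PaO2/FiO2, the P(A-a)O2 gradient and the a/A PO2 ratio. Each is compared between arms at nominal D6 and D15.

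SAP 8.1.2 fits a separate MMRM to each endpoint and tabulates "Estimates of the differences between treatments in mean change from baseline, 95% confidence interval and p-value at D6 and D15 for each endpoint". That makes six p-values. SAP 3.1 reserves p-values for the primary endpoints and gives only confidence limits for endpoints tied to secondary objectives.

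SAP 4.5 adjusts for none of this: "There are no plans to control for multiplicity in the primary objectives as the endpoints are different parameterizations of the same underlying endpoint". It then concludes that PaO2/FiO2, the sample-size endpoint, is in effect the only primary one, and singles out the comparisons at both D6 and D15 as the ones that matter. It gives no order and no success rule.

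SAP 2.4 defines the target as "the difference from baseline measured at the primary endpoint (at day 6 and day 15) between the control and the treated group" and states that "there would be >85% power to show a significant difference from standard of care at the 2 sided 5% level". Protocol 11.1 gives the same calculation.

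The protocol is not uniform on what is primary. Its summary and 3.1 name PaO2/FiO2 and the A-a gradient; 4.1 adds the a/A ratio.

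**The concern.** A level of 5% and a power figure describe a decision rule, and the plan does not state one. Even if PaO2/FiO2 is accepted as the only primary endpoint, two comparisons remain. Calling the endpoints re-expressions of one quantity may justify setting two of the three measures aside, but it does not choose between two days.

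If a significant result on either day would be reported as success, the chance of a false positive exceeds 5%. If both days must succeed, power may fall short of the stated figure. Because the trial is open-label, a choice of day made after comparative data have been seen could not be defended as independent of the results.

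There is also an internal conflict. SAP 4.5 treats PaO2/FiO2 as the only primary endpoint, while 3.1, 8.1 and 8.1.2 treat all three measures as primary and give each a p-value.

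**Working it through.** **Inputs from SAP 2.4 and protocol 11.1.** 54 v 27 patients; difference 80 in PaO2/FiO2; SD 105; two-sided 5%; dropout below 10% (10% taken as the worst case, so 48.6 v 24.3). The documents give no correlations, so those below are assumptions.

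**1. Reproduce the stated power (one endpoint, one day).**
SE = SD × √(1/n_A + 1/n_B); z = 80/SE; power ≈ Φ(z − 1.960).
- No loss: SE = 105 × √(1/54 + 1/27) = 24.75; z = 3.232; power 89.8% (normal), 89.1% (noncentral t).
- 10% loss: SE = 105 × √(1/48.6 + 1/24.3) = 26.09; z = 3.067; power 86.6% (normal), 85.7% (noncentral t).

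The figure of more than 85% is correct for a single comparison.

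**2. PaO2/FiO2, success on either day.** With no treatment effect, the error rate is 1 − P(|Z6| < 1.96 and |Z15| < 1.96), where the two statistics are bivariate normal with correlation r. Independence would give 1 − 0.95² = 9.75%.

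**3. PaO2/FiO2, success on both days.** Power is P(Z6 > 1.96 and Z15 > 1.96), with the 80-point effect present on both days (normal approximation).

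| r between days | Either-day error | Both-days power, 10% loss | Both-days power, no loss |
|---|---|---|---|
| 0.3 | 9.5% | 76.6% | 81.9% |
| 0.5 | 9.1% | 78.1% | 83.0% |
| 0.7 | 8.3% | 79.9% | 84.5% |
| 0.9 | 7.0% | 82.7% | 86.7% |

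SAP 3.2.1.3 carries the discharge measurement forward, so a patient discharged by day 6 contributes the same value at D6 and D15. That raises r and moves both columns towards the bottom of the table.

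**4. Sensitivity to the meaning of 105.** The MMRM adjusts for baseline, and the documents do not say whether 105 is a raw or an adjusted SD. If it is raw, the adjusted SD is 105 × √(1 − b²), where b is the correlation with baseline. At 10% loss, both-days power over the same range of r is then:
- b = 0.3 (SD 100.2): about 81% to 86%
- b = 0.4 (SD 96.2): about 85% to 89%

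**5. If all six p-values could count.** Independence would give 1 − 0.95⁶ = 26.5%, which is too high because the measures share one blood gas. With assumed correlations of 0.3 to 0.9 between days and 0.7 to 0.95 between endpoints on the same day, simulation gives about 10% to 20%.

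**6. Are the three measures interchangeable?** At a fixed FiO2 they differ only through PaCO2. When FiO2 changes they can diverge. By the formulas in SAP 8.1.1 (atmospheric pressure 760, water vapour 45, RQ 0.82), take an invented patient who moves from PaO2 55, FiO2 0.21, PaCO2 35 to PaO2 140, FiO2 0.50, PaCO2 40.
- Alveolar PO2: 715 × 0.21 − 35/0.82 = 107.5, then 715 × 0.50 − 40/0.82 = 308.7.
- PaO2/FiO2: 262 to 280 (better).
- A-a gradient: 52 to 169 (worse).
- a/A ratio: 0.51 to 0.45 (worse).

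**The case against.** The strongest reply is that this is a phase 2a proof-of-concept trial that protocol 11.2 calls exploratory, and that SAP 4.5 already names the one endpoint that counts. Several parts of that reply stand.

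- **Six co-equal tests.** A reader might infer from 8.1.2 that six tests share the primary claim and quote 10% to 20%. The documents do not support that as the main reading, because 4.5 and both sample-size sections point to PaO2/FiO2 alone. What stays open on the SAP's own terms is two days.
- **Interchangeability.** Protocol 9.4 makes the D6 and D15 gases mandatory after at least three minutes off supplemental oxygen, with ventilator settings used for ventilated patients. The diverging patient above would therefore have been ventilated or sampled off oxygen rules. Protocol 4.1 accepts that some patients cannot do without oxygen, but no document gives the FiO2 mix, so the frequency of divergence cannot be estimated.
- **Interim 1.** A reader might add its six p-values to the error rate. That is not justified: under SAP 4.4.1 the look cannot stop the study, so it leaves the error rate of the final tests unchanged.
- **Power.** A reader might infer that the power figure is wrong. It reproduces. No document requires success on both days, so the shortfall is conditional on that rule.
- **The a/A direction.** SAP 8.1.1 follows its notes on the other two measures with "No similar statement for a/A PO₂ is appropriate". This is a small point, since the direction of improvement follows from PaO2/PAO2.

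The exploratory label does not close the gap. SAP 4.5 applies that description to the secondary objectives, while the primary objective carries a stated 5% level and power. None of these replies supplies a rule for the two days.

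**Conclusion.** The concern holds in a limited form. The stated 5% level and >85% power are true of PaO2/FiO2 on one day, and the plan does not name the day. An either-day rule gives about 7% to 9.5% false positives, probably nearer the low end because discharge values are carried forward. A both-days rule gives about 77% to 83% power at 10% loss if 105 is the SD for the adjusted comparison; it can reach or pass 85% if 105 is a raw SD and baseline is informative. These ranges rest on assumed correlations of 0.3 to 0.9 between days.

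Separately, SAP 4.5 conflicts with 3.1, 8.1 and 8.1.2 on whether the A-a gradient and a/A ratio are primary, and that needs reconciling. For an exploratory trial the consequence is moderate, and the repair is a matter of wording.

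**What to change.** In SAP 4.5 and 8.1.2, name change in PaO2/FiO2 on one day as the primary test at two-sided 5%, and test the other day only if the first succeeds. The order is the sponsor's choice, since nothing in the documents ranks D6 against D15. It should be fixed before comparative results are seen. The documents do not show whether Interim 1 has already taken place; if it has, the SAP should say so and record when the order was set.

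Report the A-a gradient and a/A ratio as supportive, with estimates and 95% confidence intervals, and bring SAP 3.1 and 8.1 into line. In SAP 2.4 and protocol 11.1, state that the >85% power refers to the first test.

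**Cost.** No extra patients, and no loss of power for the first test. It is not an SAP-only change: the protocol's summary, 3.1, 4.1 and 11.2 give the A-a gradient a primary role, so their wording should be aligned at the next amendment, with the approval that protocol 15.3.2 requires for significant changes. The small downside is that an effect seen only on the second-ranked day cannot be claimed as a primary success.

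If the sponsor prefers an either-day rule, testing each day at 0.025 keeps the overall level within 5%, but power on each day is then 79.5% at 10% loss (normal approximation). Under a both-days rule no adjustment of the level is needed, but the power statement must be recalculated for that rule.

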4.6 Use of an efficacy subset of participants

Not applicable.

4.7 Examination of subgroups

Not applicable.

5 STUDY POPULATION CHARACTERISTICS

5.1 Participant disposition

Participants are considered **screenfails** if they were deemed not eligible for randomisation.

Since this is initially an in participant study the Nominal Days are not considered a scheduled protocol visit.

A participant who dies at any time during the study is considered as having **completed the study and primary assessment period**. If they discontinued early from planned active treatment duration (i.e. not including hospital discharge), the participant is considered as having **completed the study and primary assessment period, but not completed planned active treatment duration**.

In addition, a participant is considered to have **completed the study** if they have completed D28 and the follow-up visit. Participants can be discharged from hospital at any time, and as long as they have completed D28 and the follow-up visit, they have **completed the study**.

Participants have **completed primary assessment period** if they have:

- Arm A: completed up to 14 days of treatment with study drug followed by 14 days of either IV or oral prophylactic antibiotic treatment (as an in-participant or after discharge from hospital) AND completed D28 procedures
- Arm B: Completed up to 14 days of treatment with study drug (SOC+ 1 week of prophylactic antibiotic treatment) AND completed D28 procedures

Participants have **not completed primary assessment period**:

- are discontinued treatment prior to end of planned active treatment duration due to an adverse event - they may still complete D28 and/or follow-up visits
- discontinue treatment prior to end of planned active treatment duration as they meet an exclusion criterion (either newly developed or not previously recognized) that precludes further study treatment participation - they still may complete D28 and/or follow-up visits
- withdraw consent from being treated prior to end of planned active treatment duration – they may agree to complete D28 and/or follow-up visits
- Complete the treatment as planned but do not complete D28 procedures

Participants have prematurely **withdrawn from the study** if they:

- are lost to follow-up, after hospital discharge (i.e. do not complete D28 and follow-up visits or do not complete follow-up visit).
- Withdraw consent from being treated prior to end of planned active treatment duration and from D28 and follow-up visits

-
- Withdraw consent for D28 and follow-up visit procedures visit after completing planned active treatment duration

A listing of participants who failed screening at the beginning of the study will be presented for the ES, providing dates of informed consent and primary reason for screenfail.

In addition, the disposition of participants screened and treated will be summarized by site. This table may include, for each site, the site number, principal investigator name, the dates of the first participant in and the last participant out, the number of participants screened (ES), randomized (RS), treated (SS) and included in the FAS, PPS and PKS (if RS and PPS generated).

Disposition (completed study, completed primary assessment period, completed planned treatment duration or prematurely withdrawn from study and subsets) in each analysis set will be summarized by treatment group, and overall.

The number of participants who enrolled (overall only) and the number and percentage of screenfails (overall only) will be provided.

The following will be provided for the FAS, by treatment arm and overall.

- The number of participants randomized (used as basis for following percentages)
- The number of participants who started treatment
 - The number and percentage of participants who **complete** the study
 - Of these,
 - The number and percentage of participants who were discharged prior to D15
 - The number and percentage who died and how many of these died prior to D15
 - The number and percentage of participants who **complete the primary assessment period**
 - Of these,
 - The number and percentage of participants who were discharged prior to D15
 - The number and percentage who died and how many of these died prior to D15
 - The number and percentage of participants who **did not complete the primary assessment period**
 - Of these,
 - The number and percentage of participants who discontinued active treatment
 - Due to Adverse Event
 - Due to withdrawing consent

- Due to not meeting exclusion criteria
 - The number and percentage who did not complete D28 assessments
- The number and percentage of participants who **withdrew from study**
 - Due to lost to follow-up
 - Due to withdrawing consent
- The number and percentage who completed planned active treatment duration
- The number and percentage who completed the D28 assessment
- The number and percentage who completed 12-22 week follow-up visit
- The number and percentage of participants who died

The number and percentage of participants who discontinued due to AEs will be summarized separately for all participants, based on the FAS. This will be used for European Union Drug Regulating Authorities Clinical Trials (EudraCT) reporting.

In addition, the following listings will be presented:

- Study participant disposition (ES)
- Study discontinuation (ES)
- Analysis sets (ES)

The listing of study participant disposition will be presented by treatment group and by site, and will include the date of informed consent, date and time of first and last dose of study treatment, number of days on treatment, date of decision to terminate study treatment early and primary reason, date of D28 visit, date of the follow-up visit (if completed).

The number of days on study treatment will be calculated as follows:

$$\begin{aligned} & \textit{Number of Days on Study Treatment} \\ & = (\textit{Date of Last Dose Received} - \textit{Date of First Dose Received}) + 1 \end{aligned}$$

5.2 Protocol deviations

Important protocol deviations will be identified and classified by the deviation types defined in the IPD document, as per Section 3.4.

A listing of all IPDs identified at a data review meeting and will be presented for all study participants based on the FAS and will include the deviation type and description. The number and percentage of participants in the FAS with IPDs will be summarized by treatment group and for all participants for each deviation type. The number and percentage of participants who were excluded from the PPS will also be presented. The denominator for the percentage calculations will be the number of participants in the FAS.

6 DEMOGRAPHICS AND OTHER BASELINE CHARACTERISTICS

Additional endpoints to those mentioned below may be collected at baseline and will be summarized appropriately.

6.1 Demographics

A by-participant listing of demographics will be presented based on the ES. This will include the year of birth, age (calculated in years from date of randomisation), sex, race, height (in cm), weight (in kg) and body mass index (BMI, in kg/m²). The height will be the measurement obtained at the Screening visit. Weight will be the last non-missing value prior to the first dose of study treatment.

The BMI will be derived using the height and weight measurements recorded at the Screening visit and will be reported to 1 decimal place.

All demographic characteristics will be summarized by treatment group using the FAS. The summary of age will include descriptive statistics and categorical summaries, the latter based on requirements for EudraCT and clinicaltrials.gov reporting.

For the EudraCT reporting, the categories will include:

- 18 to <65 years
- 65 to <85 years

For clinicaltrials.gov reporting, the categories will include:

- ≤18 years
- 19 to <65 years
- ≥65 years

No statistical analysis will be performed on demographic data.

6.2 Other Baseline characteristics

All other baseline characteristics collected based on eligibility criteria will be listed for the FAS.

The following baseline characteristics will be summarized by treatment group using the FAS

COVID-19 tests

- Number and percentage on COVID-19 ward and ICU
- Number and percentage with positive PCR for COVID-19
- Number and percentage of Multiple PCRs
- Number and percentage of each type of sampling for COVID-PCR
 - Nasopharyngeal
 - BAL (bronchoalveolar lavage)
 - Anal

- Sputum
- Blood
- Urine
- Other (specify)
- Number and Percentage of PCR for other micro-organisms
 - Number and percentage positive for
 - Influenza
 - RSV
 - Other (Specify)
- Number and percentage of positive antigen tests for COVID-19
- Number and percentage of serology/other validated COVID-19 diagnostic tests

- Number and percentage of hypoxic respiratory failure

BASELINE ORDINAL SCALE Category

- Number and percentage with each score: 1 Death, 2 Hospitalized, requiring ECMO, invasive mechanical ventilation, or both, 3 Hospitalized, requiring nasal high-flow oxygen therapy, non-invasive mechanical ventilation, or both, 4 Hospitalized, requiring supplemental oxygen, 5 Hospitalized, not requiring supplemental oxygen, 6 Not hospitalized
- Note: these are worded slightly differently on the CRF

CYTOKINE RELEASE SYNDROME

- Summary of absolute score and probabilities for presence of sHLH by treatment arm (involves mapping the provided HScore to the appropriate point on the probability scale using linear interpolation to a probability based on the information contained in the following table)

HScore	Probability of hemophagocytic syndrome
≤90	<1%
91-100	~1%
101-110	1-3%
111-120	3-5%
121-130	5-9%

131-140	9-16%
141-150	16-25%
151-160	25-40%
161-170	40-54%
171-180	54-70%
181-190	70-80%
191-200	80-88%
201-210	88-93%
211-220	93-96%
221-230	96-98%
231-240	98-99%
≥241	>99%

Note: the best cutoff value for HScore was 169, corresponding to a sensitivity of 93%, specificity of 86%, and accurate classification of 90% of the participants.

Reference: <https://www.mdcalc.com/hscore-reactive-hemophagocytic-syndrome#evidence>

- Number and percentage of BOTH highly suspect bilateral ground opacities on chest CT-scan AND typical clinical and chemical diagnosis with signs of cytokine release syndrome
- Number and percentage of Radiography showing bilateral infiltrates in last 2 days (should be 100%)
- Number and percentage of signs of Cytokine Syndrome (should be 100%)
 - As shown by:
 - Number and percentage of single ferritin >2000 ng/ml (denominator participants with high flow nasal oxygen or mechanical ventilation i.e. total of participants on ordinal score 2 or 3 (which should be our participant population)) OR
 - Number and percentage of Ferritin > 1000 ng/ml and rising since last 24 hours
OR
 - Lymphopenia < 800 /μL AND ≥ 2 of:
 - Ferritin > 700 mcg/L and rising since last 24h

- CRP > 70 mg/dL and rising since last 24h without bacterial infection
- LDH > 300 IU/L and rising since last 24h
- D-dimers > 1000 ng/mL and rising for 24h

OR

- Lymphopenia < 800 / μ L AND \geq 3 of:
 - Ferritin > 700 mcg/L
 - CRP > 70 mg/dL
 - LDH > 300 IU/L
 - D-dimers > 1000 ng/mL

Summary statistics and distribution plots of laboratory parameters listed here will be provided by treatment arm.

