6.1. Inclusion Criteria

-Recent (≥ 6 days and ≤ 16 days of flu-like symptoms or malaise prior to randomization) infection with COVID-19.

-COVID-19 diagnosis confirmed by antigen detection test and/or PCR and/or positive serology, or any emerging and validated diagnostic laboratory test for COVID-19 within this period. For patients with a negative SARS-CoV-2 PCR and either a positive SARS-CoV-2 antigen or antibody test, the presence of suggestive lesions for COVID-19 on chest-CT scan is mandatory.

-In some patients, it may be impossible to get a confident laboratory confirmation of COVID-19 diagnosis after 24h of hospital admission because viral load is low and/or problems with diagnostic sensitivity. In those cases, in absence of an alternative diagnosis, and with highly suspect bilateral ground glass opacities on recent (< 24 h) chest-CT scan (confirmed by a radiologist and pulmonary physician as probable COVID-19), and a typical clinical and chemical diagnosis with signs of cytokine release syndrome, a patient can be enrolled as probable SARS-CoV-2-infected. In all cases, this needs confirmation by later seroconversion.

-Presence of hypoxia defined as

1) O₂ saturation below 93% on minimal 2l/min O₂ therapy;
and/or

2) PaO₂/FiO₂ below 350 mmHg (Strongly recommended: patient in upright position, after minimal 3 minutes without supplemental oxygen; In ventilated patients PaO₂ can be taken from invasive arterial line and FiO₂ taken directly from mechanical ventilation settings).

-Signs of acute lung injury and/or cytokine release syndrome defined as

ANY of the following

-serum ferritin concentration > 1000 mcg/L and rising since last 24h

-single ferritin above 2000 mcg/L in patients requiring immediate high flow oxygen device (Optiflow) or non-invasive or invasive mechanical ventilation

-lymphopenia defined as < 800 lymphocytes/microliter and two of the following extra criteria

-Ferritin > 700 mcg/L and rising since last 24h

-increased LDH (above 300 IU/L) and rising since last 24h

-D-Dimers > 1000 ng/mL and rising since last 24h

-CRP above 70 mg/L and rising since last 24h and absence of bacterial infection

-if three of the above are present at admission, no need to document 24h rise

-Low dose Chest CT or HRCT or Angio Chest CT scan showing bilateral infiltrates within last 2 days prior to randomization

-Admitted to specialized COVID-19 ward or an ICU ward taking care of COVID-19 patients

-Age ≥ 18 years

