3.3 Protocol deviations

Important protocol deviations are deviations from the protocol which potentially could have a meaningful impact on study conduct or on the primary efficacy (effectiveness) or safety for an individual participant. The criteria for identifying important protocol deviations may be defined within the appropriate protocol-specific document. Important protocol deviations will be reviewed as part of the ongoing data cleaning process and data evaluation documented in a protocol deviation log. All important deviations will be identified and documented prior to final database lock to confirm exclusion from analysis sets.

Note: whilst protocol deviations maybe listed for Interim1 it is unlikely sufficient determination on the effect of the deviations will have been reviewed and hence no one will be excluded from the PPS (section 3.5.6) for Interim1.

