4 STATISTICAL/ANALYTICAL ISSUES

4.1 Adjustments for covariates

Covariates such as sex, age, BMI (measure of obesity) and race may also be included in the models if by the time of analysis these have been identified as key differentiators in terms of COVID-19 recovery.

Weight may also be used (independently of BMI) as a covariate to explore the impact of weight on results as the usual dosing regimen for Zilucoplan® is to dose by weight.

In addition, the impact on the results of disease severity at baseline may be explored using the 4 middle categories of the 6 point ordinal scale to define disease severity at baseline as a covariate

Where indicated, some secondary endpoints will explore the impact of baseline laboratory values on efficacy endpoints eg Baseline D-Dimers and C5a values.

The addition of the interaction of any baseline covariate with treatment may be explored to identify any evidence to suggest a differential impact on results.

Prior to fitting any model, all data will be explored graphically.

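### SAP 6.2 restates the protocol's CRP entry threshold of 70 mg/L as 70 mg/dL, ten times higher, in both lymphopenia routes of the baseline cytokine release summary

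*SAP*

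**What the plan says.** Protocol 6.1 requires signs of acute lung injury or cytokine release, shown by any one of several routes. Two routes rest on ferritin alone: "serum ferritin concentration > 1000 mcg/L and rising since last 24h", or a single value above 2000 mcg/L in a patient who needs high-flow oxygen or ventilation. The third is "lymphopenia defined as < 800 lymphocytes/microliter and two of the following extra criteria". Its four extra criteria are ferritin, LDH, D-dimers and CRP, and the CRP item reads "CRP above 70 mg/L and rising since last 24h and absence of bacterial infection". The protocol then relaxes the need for a documented rise: "if three of the above are present at admission, no need to document 24h rise".

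SAP 6.2 turns this into a baseline summary by treatment group on the Full Analysis Set and notes that the overall row ought to come to 100%. It splits the lymphopenia route in two: at least two markers with a rise, or at least three without one. In the first list the CRP item is "CRP > 70 mg/dL and rising since last 24h without bacterial infection". The second list gives the same number and unit, without the rise.

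In the same block, the denominator of the single-ferritin row is described as "total of participants on ordinal score 2 or 3 (which should be our participant population".

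**The concern.** The SAP is meant to restate an entry criterion here, not to set a new one, so the two thresholds should be identical. They differ by a unit prefix, and the difference is ten-fold. The row also works as a check on the enrolled population, because the SAP states in advance what the answer should be. A programmer who follows the SAP literally could produce a figure below 100% for a correctly enrolled population. The shortfall would then look like an enrolment problem when its cause is the analysis specification.

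**Working it through.** **Step 1: compare the thresholds.** Conversions used: 1 ng/mL = 1 mcg/L and 1 L = 10 dL.

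| Item | Protocol 6.1 | SAP 6.2 | Same after conversion? |
|---|---|---|---|
| Lymphocytes | below 800 per microlitre | below 800 per microlitre | yes |
| Ferritin, rising | 1000 mcg/L | 1000 ng/mL | yes |
| Ferritin, single value | 2000 mcg/L | 2000 ng/mL | yes |
| Ferritin, lymphopenia route | 700 mcg/L | 700 mcg/L | yes |
| LDH | 300 IU/L | 300 IU/L | yes |
| D-dimers | 1000 ng/mL | 1000 ng/mL | yes |
| CRP | 70 mg/L | 70 mg/dL (twice) | no |

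For CRP: 70 mg/dL × 10 dL/L = 700 mg/L, and 700 / 70 = 10. In the other direction, the protocol's 70 mg/L is 7 mg/dL. The SAP figure does not reproduce the protocol figure.

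**Step 2: rule out a version difference.** SAP section 1 says it is based on protocol version 3.0. The amendment log entries for versions 4.0, 5.0 and 6.0 list no change to the CRP entry item, so the version gap does not explain the mismatch.

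**Step 3: see which CRP values change class.** Values of 71, 150, 300, 500 and 700 mg/L meet the protocol item and fail the SAP item. A value of 701 mg/L meets both. The affected range is above 70 and up to 700 mg/L.

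**Step 4: see which marker patterns change class.** Take a lymphopenic participant whose CRP, when positive by the protocol, lies in that range. Each of the four markers is present or absent.

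- At least two markers: C(4,2) + C(4,3) + C(4,4) = 6 + 4 + 1 = 11 qualifying patterns. Those with CRP and exactly one other marker are lost: C(3,1) = 3. So 3 of 11 are lost.
- At least three markers: C(4,3) + C(4,4) = 4 + 1 = 5 qualifying patterns. Those with CRP and exactly two others are lost: C(3,2) = 3. So 3 of 5 are lost.

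These are counts of logical patterns within each route, not proportions of patients.

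**Step 5: allow for the other routes.** The routes are joined by OR, and a participant is misclassified only if all of them fail. Someone with CRP and two other markers who drops out of the three-marker route still qualifies by the two-marker route if those two others are rising. Someone with CRP and one other rising marker still qualifies if the three non-CRP markers are all above threshold. Either ferritin-only route also rescues the participant. The documents give no CRP distribution and no joint distribution of the markers, so the number left misclassified cannot be calculated and could be zero.

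**The case against.** The mismatch itself is hard to dispute. The case on the other side concerns its consequences, and much of it stands.

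- **Programming is not specified.** SAP 6.2 does not say whether the flag is re-derived from laboratory values or copied from an eligibility response in the eCRF. In the second case the counts are right and only the row label is wrong. This stands, so the misclassification is conditional.
- **Per Protocol Set.** A reader might infer that false ineligibility would remove participants from this set, since SAP 3.3 says "All important deviations will be identified and documented prior to final database lock to confirm exclusion from analysis sets". The documents do not support that step. Deviations are identified through data cleaning, a deviation log, a separate deviation document and a data review meeting (SAP 3.3 and 5.2), and nothing feeds the 6.2 table into that process.
- **Reported CRP.** A reader might infer that the share with raised CRP would be misreported. SAP 6.2 plans no stand-alone CRP percentage. CRP enters only as a component of the two lymphopenia routes, and its actual values are summarised and plotted separately.
- **A threshold almost never reached.** A reader might also infer this of 700 mg/L. It needs a CRP distribution that the documents do not give.
- **Self-check.** The SAP's expected 100% would make a shortfall visible and prompt a query. That limits the harm, but the query would have been created by the SAP's own error.
- **Ordinal score 2 or 3.** A reader might take the parenthetical as narrowing the trial population. It sits on the denominator of the single-ferritin row, where scores 2 and 3 fit the protocol's restriction to high-flow oxygen or ventilation. It defines no analysis set and changes no result.

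**Conclusion.** SAP 6.2 is wrong as written: in two places its CRP threshold is ten times the protocol criterion that it restates. The effect on results is narrow and conditional. It arises only if the flag is derived from laboratory values with the printed cut-off, and only for participants with CRP above 70 and up to 700 mg/L who need CRP to reach the marker count and qualify by no other route. Otherwise the fault is a wrong label. Enrolment follows the protocol. Full Analysis Set membership needs only a dose of study treatment (SAP 3.5.4), and the primary MMRM does not use this flag. The point therefore concerns one descriptive baseline summary and does not bear on the efficacy estimates. It merits correction because the row is meant to verify the enrolled population and the correction is trivial.

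**What to change.** Reconcile both CRP lines in SAP 6.2 with the threshold and unit in protocol 6.1 (mg/L). Before the flag is programmed, confirm that the eCRF and the table shells use the same unit, and state whether the flag is derived from laboratory values or taken from a recorded eligibility response. The cost is two unit corrections and one check.

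As optional tidying with no numerical effect, remove the remark that scores 2 or 3 should be the participant population and keep those scores only as the denominator of the single-ferritin row. Protocol 6.1 does not require high-flow oxygen or ventilation for entry, and SAP 4.1 uses the "4 middle categories of the 6 point ordinal scale to define disease severity at baseline".
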